5. The link will take you to the Project Summary page for the project. Follow the PI instructions for items #4 and #5 above.

If you are a contact (member of research team) and you wish to access minutes or approved materials:

1. Login to the regular myIRB website as yourself.
2. Scroll to the listing of "Projects" at the bottom of your Inbox page.
3. Change the filter for the Project to show projects where you are a research team member and click "Go" on the filter.
4. Click on the IRB number for the approved project.
5. The link will take you to the Project Summary page for the project. Follow the PI instructions for items #4 and #5 above.

E1 Overview or Design Summary

ED patients will be approached for informed consent if they meet selection criteria. Patients who consent to be in the trial will be randomized to either morphine (0.1mg/kg maximum dose of 10 mg) or ketamine (0.4 mg/kg, maximum dose of 40 mg). During the consent process, patients can be pretreated for pain with fentanyl IV up to 100mcg. Patients will not be given their assigned pain medication until at least thirty minutes after administration of any fentanyl to avoid overlapping effect of fentanyl with ketamine or morphine.

~~ED patients will be approached for informed consent if they meet selection criteria. Patients who consent to be in the trial will be randomized to either morphine (0.1mg/kg maximum dose of 10 mg) or ketamine (0.4 mg/kg, maximum dose of 40 mg).~~

PHARMACY NOTIFICATION

The research pharmacy will be notified of a potential study participant so they can prepare to randomize the participant using a random number generator. Odd numbered participants will receive ketamine and even numbered participants will receive morphine. Participants in the low dose ketamine arm will receive 0.4 mg/kg IV of ketamine (40 mg maximum). Participants in the opioid arm will receive 0.1 mg/kg of morphine up to 10 mg.

PHARMACY FORMULATION

Upon the completion of consent, the pharmacy will be notified to draw up the appropriate medication and send the medication to the Emergency Department. The study medication will be in identical appearing unmarked syringes, so that neither the study team nor the study subject will know which medication is being administered.

VITAL SIGN COLLECTION

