The research coordinator will then complete page one of the Ketamine Data Form. This includes the participant's medical history, including a history of drug abuse, or prior narcotic use, a description of the injury, prior medications given to the subject for this injury either by EMS or in the emergency department, baseline vital signs (prior to study drug administration) and the time of study drug administration. Page 2 includes the baseline (pre study drug administration) visual analog pain scale that the participant will complete.

MEDICATION ADMINISTRATION

If the participant has not yet had an IV placed, one will be placed by the nurse caring for the participant at this time. Study drug will then be administered.

VITAL SIGN COLLECTION

The participant's heart rate, blood pressure, respiratory rate and oxygenation saturation (by pulse oximetry) will be collected every 5 minutes for the first 30 minutes, and every 10 minutes

for the next 30 minutes. The study will terminate at the end of 60 minutes and a final set of vital signs will be recorded at that point on Page 3 of the Ketamine Data Form.

REEVALUATION & EXIT SURVEY

The participant will be asked to complete repeat visual analog pain scales at 15, 30, and 60 minutes following study drug administration. The VAS will be administered by a second study coordinator, who has been blinded to the vital sign information, since blood pressure response may allow unblinding to occur. The participant will not have access to their original score for comparison. The study coordinator will then complete the post treatment survey on Page 5. The participant will continue to receive standard care by the emergency department physicians and nurses to ensure adequate relief of pain, appropriate treatment of the underlying pathology, hemodynamic and neuropsychiatric stability, and appropriate diagnostic evaluation, disposition, and follow-up. Any adverse events that occur during the continued treatment of the participant until either admission or discharge will be recorded.

RESCUE MEDICATION

Subjects that do not obtain adequate pain relief within 15 minutes of study drug administration will be offered rescue medication with intravenous morphine sulphate at the same weight-based dose (0.01mg/kg; maximum 10 mg)

TREATMENT OF ADVERSE EVENTS AND SERIOUS ADVERSE EVENTS

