Adverse events and serious adverse events will be noted on the data form and treated by the study physician or the primary treating physician as medically indicated.

E2 Subject Selection and Withdrawal

2.a Inclusion Criteria

Patients over the age of 18 presenting with long-bone fractures are eligible for enrollment. Eligible long-bone fractures include fractures of the shaft of the humerus, radius, ulna, femur, tibia, and fibula.

2.b Exclusion Criteria

Patients with injuries older than 24 hours will be excluded. Patients with avulsion fractures will be excluded. Patients with a history of substance abuse, chronic opioid dependence, pregnancy, intoxication, allergy to ketamine or opioids, and those that cannot consent (e.g. active mental disease preventing them from having capacity to consent) will be excluded. Any patients with hemodynamic instability defined as systolic blood pressure > 180 mmHg or < 100 mmHg, heart rate > 130 bpm, respirations < 10 rpm, or oxygen saturations on room air < 90% shall also be excluded. In addition, any patient that received a narcotic analgesic aside from fentanyl within the last 2 hours will be excluded.

2.c Study Termination

Subjects can terminate their participation in the study at any time. The alternative to continuing in the study is to have the pain treated by emergency physicians and staff as per usual care. The study physician may terminate the study prior to the specified endpoint when deemed medically prudent to do so.

2.d Ethical Considerations

Current research has investigated the effectiveness of ketamine as an analgesic in the Emergency Department. Much of that research is observational which limits the conclusions that can be drawn. While ketamine's mechanism of action would be consistent with an agent that can result in analgesia, we would like to conduct a randomized, blinded trial to determine if ketamine is as effective as an analgesic as morphine. We believe given the pharmacologic properties of ketamine, and prior published research, that ketamine is an effective analgesic so this research is important and ethical. All data will be collected by trained research staff and kept in a locked office to minimize the chance of lost data.

2.e Subject Recruitment Plans and Consent Process

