Patients who are identified as potential study participants will be approached by the research coordinators regarding informed consent. The purpose of the study, study procedures, and associated risks and benefits will be explained to the potential subject. Following this, subjects will have 10 minutes to review the consent form on their own and if they agree to participate in the study, the consent form will be completed.

2.f Randomization Method and Blinding

Randomization will occur in the research pharmacy using opaque, sealed envelopes. Twenty participants will be randomized into each arm. Participants in the LDK arm will receive 0.4 mg/kg IV of ketamine (40 mg maximum). Participants in the opioid arm will receive 0.1 mg/kg of morphine up to 10 mg. Medications will be prepared by the pharmacy and delivered to the treating nurse in identical syringes. Study drug will be blinded to the research team and the study participant.

2.g Risks and Benefits

Patient will be exposed to medical risks in both conditions. Patients exposed to morphine will be at risk for hypotension, respiratory depression, altered mental status and possible allergic reaction. Patients exposed to ketamine will be at risk for hypertension, dysphoria and in rare cases laryngospasm and emergence reaction. These side effects are well known by practitioners since both of these drugs are regularly given in the Emergency Department. Patients may also be at risk for inadequate pain control in either condition.

2.h Early Withdrawal of Subjects

Participants will be told they have the right to withdraw from the study at anytime for any reason. Participants will also be taken out of the study early if the physician, nurse or research coordinator decides that the participant is at risk for a life-threatening event. Since this study does not include any outpatient follow-up, we do not anticipate early withdrawal to be a problem.

2.i When and How to Withdraw Subjects

The research coordinator will continually monitor the participant, and the nurses and physicians will be able to remotely monitor the participant's vital signs at the telemetry station. If a life-threatening event is identified, the participant will be resuscitated as deemed appropriate by the physician caring for the participant.

2.j Data Collection and Follow-up for Withdrawn Subjects

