Due to the short duration of the study (60 minutes), we do not anticipate early withdrawal to be a problem. Participants who have inadequate pain relief and require rescue medication, or who have adverse events that require other treatment will have their data included, even if study personnel are unable to complete the follow-up VAS scores at 15, 30, or 60 minutes.

Study Drug

2.k Description

Ketamine is a dissociative agent that is thought to modulate pain by binding to NMDA receptors. Participants assigned to the ketamine arm will be given 0.4 mg/kg IV of ketamine (40 mg maximum).

Morphine is an opioid that acts on opioidergic receptors to modulate pain. Participants in the opioid arm will receive 0.1 mg/kg IV of morphine (10 mg maximum).

2.l Treatment Regimen

The study is designed to compare a one-time dose only. Therefore study medication administration will occur once following the baseline pain and vital sign assessment.

Assignment of Subjects to Treatment Groups

Participants will be assigned to either the ketamine arm or the morphine arm in the pharmacy by random number generator. Participants and all study personnel will be blinded to the assignment.

2.m Preparation and Administration of Study Drug

Once participants are in the process of being consented, the pharmacy will be notified to prepare the drug. The drug will then be sent to the Emergency Department for administration.

2.n Subject Compliance Monitoring

Participants will be given the drug intravenously by the emergency department staff nurse assigned to their care. The research coordinator will monitor the participant's vital signs, pain relief, and any side effects during the duration of the study. Since medication is only given one time, non-compliance will not be an issue.

Prior and Concomitant Therapy

Participants will be excluded from the study if they are found to be chronic users of either prescribed or illicit opioids or opiates.

2.o Packaging

Study drug will be packaged by the pharmacy in identical looking syringes so as to maintain blinding. This is a question for the pharmacy. I will email [name] about this.

2.p Blinding of Study Drug

As above

2.q Receiving, Storage, Dispensing and Return

The pharmacy will transport the study medication to the emergency department. If the patient withdraws from the study, the medication can be returned to the pharmacy.

F Study Procedures

F1 Screening for Eligibility

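### The 2.b look-back for prior analgesia covers recent morphine but not recent ketamine, the other study drug, and its fentanyl exemption is not reconciled with E1

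*SAP*

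**What the plan says.** The eligibility rule on recent analgesia is in SAP 2.b: "any patient that received a narcotic analgesic aside from fentanyl within the last 2 hours will be excluded". The only exclusion there that names ketamine is "allergy to ketamine or opioids". The section on prior and concomitant therapy deals with chronic opioid use, and F1 does not mention earlier analgesia.

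Section 2.k separates the two study drugs by class. Morphine is called an opioid. Of ketamine it says: "Ketamine is a dissociative agent that is thought to modulate pain by binding to NMDA receptors". Section 2.g notes that "both of these drugs are regularly given in the Emergency Department".

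Fentanyl is handled in E1. "During the consent process, patients can be pretreated for pain with fentanyl IV up to 100mcg". E1 then adds a wait: "Patients will not be given their assigned pain medication until at least thirty minutes after administration of any fentanyl", with the stated aim "to avoid overlapping effect of fentanyl with ketamine or morphine".

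Page one of the data form, described in E1, records "prior medications given to the subject for this injury either by EMS or in the emergency department". No eligibility rule refers to that record.

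**The concern.** The trial compares a single dose of each of two drugs (2.l). A look-back on prior analgesia keeps earlier treatment out of that comparison. The one in 2.b does so for morphine and the other narcotics it covers, but is silent on ketamine.

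A patient with ketamine still active who is allocated morphine shows the effects of both drugs. One who is allocated ketamine receives it on top of an earlier amount that the study maximum does not count. Either way the baseline VAS may already be lowered. Section 2.a sets no minimum pain score, so there may be little room left for change.

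Safety attribution is touched as well. Section 2.g lists hypertension and emergence reaction among the risks of ketamine. Section 5.c makes systolic pressure above 180 mmHg and emergence reaction SAEs, and five SAEs lead to suspension and a board review (5.b). An event caused by ketamine given before enrolment could be credited to either arm and count toward that five.

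**Working it through.** The plan has no figure to reproduce here. G1 bases the sample size on funding, with no effect size or variance. The check is mainly textual.

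**Step 1. What each kind of prior treatment meets in the rules.**

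| Prior treatment | 2.b look-back | Other rules | Result as written |
|---|---|---|---|
| Morphine within 2 hours | Covered | None needed | Excluded |
| Recent ketamine | Not covered, given the class stated in 2.k | Allergy (2.b); chronic opioid use (prior therapy section); intoxication, capacity and vital-sign limits (2.b); alertness and stability (F1) | Eligible unless visibly affected |
| Fentanyl during the consent process | Exempt | 100 mcg IV limit and 30-minute wait (E1) | Eligible, limited |
| Fentanyl earlier, from EMS or the ED | Exempt | 30-minute wait (E1); the limit is not worded to reach it | Eligible, no stated amount |

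**Step 2. Do the general criteria close the ketamine gap?** Not fully. The plan itself expects participants to complete a VAS 15 minutes after 0.4 mg/kg of ketamine. A patient who has had an analgesic dose may therefore be alert enough to be approached and to consent.

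**Step 3. Direction of the effect.** Treatment before enrolment cannot depend on allocation. Let K of the 40 participants be pretreated, with 20 per arm (2.f), and let X of them fall in the ketamine arm. X is hypergeometric with mean K/2, so the expected between-arm difference is 2 × K/2 − K = 0.

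If a fraction p of participants is affected and each contributes a contrast reduced by a fraction a, the expected contrast is δ(1 − p·a), where δ is the contrast without prior ketamine. The documents give neither p nor a, so the dilution cannot be sized.

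**Step 4. Chance imbalance at 20 per arm.** The values of K are assumptions, and K = 0 is equally consistent with the text.

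- K = 1: the arms always differ by 1/20 = 5 percentage points.
- K = 2: both fall in the same arm (10 points) with probability 2·C(20,2)/C(40,2) = 380/780 = 0.49.
- K = 4: all fall in the same arm (20 points) with probability 2·C(20,4)/C(40,4) = 9,690/91,390 = 0.11.
- K = 8, 12 or 20: the chance of a difference of 4 or more patients (20 points) is 0.24, 0.30 or 0.34. This sums C(20,x)·C(20,K−x)/C(40,K) over |2x − K| ≥ 4. Values this high are more relevant to prior analgesia of any kind, including the fentanyl that E1 permits, than to ketamine alone.

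**Step 5. Fentanyl.** The 30-minute wait applies to any fentanyl, whatever its source. The 100 mcg limit is tied to the consent process. 2.b exempts fentanyl with no limit and no reference to E1. The text does not settle whether an amount given earlier counts toward the limit.

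**The case against.** The strongest reply has four parts.

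First, 2.b contradicts nothing about ketamine. It is silent, and only the SAP is at hand. But the look-back rule is stated in this document and, followed literally, treats the two study drugs differently. That is a rule fixed badly, not detail left to another document.

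Second, other steps help. The intoxication, capacity, blood-pressure and alertness criteria screen out overt effects. The consent explanation, ten minutes of reading and drug preparation all lengthen the interval. This stands in part: these steps narrow the gap but are not a look-back.

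Third, prior ketamine may be rare or absent. Regular ED use of the drug does not show use before enrolment for fracture pain. This stands, and no frequency is claimed here.

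Fourth, randomization, a VAS taken just before study drug and a record of prior medications all limit the harm in a pilot that looks for trends. This stands too. A reader might infer that the comparison is biased toward one arm, but the documents do not support that, because the expected imbalance is zero.

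A reader might also infer that earlier ketamine makes the allocation easier to guess. The reverse is more likely: its effects can appear in either arm, so they say less about the assignment.

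Nor do the documents show that fentanyl is uncontrolled or that E1's aim is defeated. The 30-minute wait is the means E1 chose, and a patient beyond 30 minutes complies with it. The documents do not say whether that wait suffices for a larger earlier amount.

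**Conclusion.** The point holds as a cheap improvement. Followed as written, 2.b bars recent exposure to one study drug and admits recent exposure to the other, and no other section fully closes that gap. The consequences are a diluted contrast in VAS change, less certain attribution of two kinds of SAE, and chance imbalance in arms of 20.

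The size is unknown. Each affected participant is 5% of an arm, but the documents do not give the number. The conclusion rests on reading narcotic in 2.b as not including ketamine, which 2.k supports, and on some recently treated patients being alert enough to enrol. Dilution further assumes that earlier ketamine narrows the difference between arms.

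The fentanyl point is secondary. It is an unreconciled wording between 2.b and E1 about which fentanyl the limit counts, not evidence that fentanyl effects reach the comparison.

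**What to change.** - In 2.b, word the look-back so that it covers prior exposure to either study drug. The study team should set the ketamine interval; the documents give no basis for a particular value.
- Check the rule before allocation, against the EMS and ED medications that page one of the data form already collects. E1 describes page one after the pharmacy steps, so that item would need to be asked earlier. The existing narcotic rule already needs the same information at screening.
- Reconcile 2.b with E1 by stating whether fentanyl given earlier by EMS or in the ED counts toward E1's limit, and cross-refer the two sections. Which rule applies is for the study team.

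The cost is a sentence or two and one screening check on data already collected. The downside is that a few patients with prior ketamine become ineligible, a real but small loss in a trial of 40.

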Based on past research, we believe adverse events will be rare and severe events are unlikely to occur.

5.e Data Collection Procedures for Adverse Events

The research coordinator will write down all adverse events on the data form in the designated spot. They will also report the events to the treating team.

5.f Reporting Procedures

The research coordinator will report all adverse events to the principal investigator (PI) investigator during the study. The PI will determine severity and causality. The PI will keep track of adverse events to determine if the study needs to be stopped.

5.g Adverse Event Reporting Period

This is an acute treatment trial, with a duration of one hour following study drug administration. However, any AEs that occur at any time during the entire ED stay of the study participant will be reported.

Post-study Adverse Event

The duration of the drugs used in this study will not exceed the time the participant is monitored.

F6 Study Outcome Measurements and Ascertainment

Study outcomes involve change in participants' pain as measured by the VAS, significant changes in any vital signs collected, a list of adverse events that the participant experienced, as well as questions included in the data form assessing whether the participant would consider using the drug given to them for pain relief in the future.

G Statistical Plan

G1 Sample Size Determination and Power

Sample size for this study is based on limited funding and will serve as a pilot study looking for trends in the efficacy of morphine and ketamine to treat pain as well physiologic effects and adverse events. If the results appear promising, further funding will be requested and a full power analysis will be performed.

G2 Interim Monitoring and Early Stopping

All adverse events will be promptly reviewed by the primary research team following the participant's completion of the study. Any adverse event directly linked to administration of either ketamine or morphine that results in permanent disability or death will result in the cessation of the entire study. After every 10 patients are enrolled, adverse event information will be reviewed by an independent expert. If there is a high frequency of

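### Does the aim stated under Ethical Considerations (2.d) promise more than the funding-limited pilot in G1 can deliver, so that it must be reworded?

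*SAP*

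**What the plan says.** Section 2.d (Ethical Considerations) comments on earlier emergency-department work with ketamine: "Much of that research is observational which limits the conclusions that can be drawn". It then says the team would like to run a randomized, blinded trial "to determine if ketamine is as effective as an analgesic as morphine".

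G1 (Sample Size Determination and Power) sets the scale: "Sample size for this study is based on limited funding and will serve as a pilot study looking for trends in the efficacy" of the two drugs, together with their physiologic and adverse effects. It continues: "If the results appear promising, further funding will be requested and a full power analysis will be performed".

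Section 2.f (Randomization Method and Blinding) gives the number: "Twenty participants will be randomized into each arm". F6 gives the efficacy outcome: "Study outcomes involve change in participants' pain as measured by the VAS". F2 schedules the pain scale at baseline and at 15, 30 and 60 minutes.

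No significance level, power, SD, margin or analysis method for the pain comparison appears in the text available, which ends partway through G2.

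**The concern.** Section 2.d faults earlier research for the weakness of its conclusions and offers this trial as the remedy. Read literally, its aim is a non-inferiority or equivalence question, and a non-significant difference does not answer such a question. G1 promises only a first look. A reader who took 2.d as the objective and ignored G1 could treat a null result from 40 patients as evidence that the drugs relieve pain equally well.

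The stake would be an unsupported efficacy claim. With 20 per arm, a non-significant result is compatible with a sizeable deficit for ketamine, so the gap between the two sections looks like more than style.

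**Working it through.** **Inputs.** From the SAP: 20 per arm (2.f), change in VAS pain (F6), and no allowance for dropout, since for a 60-minute study "we do not anticipate early withdrawal to be a problem" (2.j). Assumed, because the text gives no figure: a two-sample t comparison with common SD, two-sided 5% (one-sided 2.5% for non-inferiority), and complete data.

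**The plan's own figure.** There is none to reproduce. Twenty per arm comes from the budget, not from a calculation.

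**Precision.** SE = SD × √(2/20) = 0.3162 SD. With 38 degrees of freedom, t(0.975) = 2.0244. The 95% CI half-width is 2.0244 × 0.3162 = 0.640 SD.

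**Margin for 80% non-inferiority power, true difference zero.** By normal approximation: (1.960 + 0.842) × 0.3162 = 0.886 SD. By the noncentral t: 0.909 SD.

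**Chance that a real deficit is non-significant (noncentral t, two-sided 5%).**

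| True deficit | Noncentrality | P(non-significant) |
|---|---|---|
| 0.5 SD | 0.5/0.3162 = 1.58 | 0.662 |
| 1.0 SD | 1.0/0.3162 = 3.16 | 0.131 |

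**In millimetres.** On an assumed 100 mm scale with an assumed SD of 15 to 30 mm, the half-width runs from 0.640 × 15 = 9.6 mm to 0.640 × 30 = 19.2 mm. A true 13 mm deficit would be non-significant in 24% to 73% of trials. That spread comes from the assumed SD, so the millimetre figures do not size the problem.

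**Does the document turn this imprecision into a wrong conclusion?**

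| Section | Role | What it commits the trial to |
|---|---|---|
| 2.d | Ethics rationale | Nothing testable: no hypothesis, margin or decision rule |
| G1 | Sample size and inference | A pilot, with a powered study to follow |
| 2.f | Allocation | 20 per arm |
| F6 | Outcomes | Change in VAS pain |

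The section that governs inference is also the section that limits it. The calculations show that 20 per arm is small, which G1 concedes by calling the study a pilot. Every figure above would be the same if 2.d were rewritten.

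**The case for a change.** The best case for a change is that 2.d is not idle text. It is the nearest thing, in the text available, to a stated comparative aim; it supports the claim that the research is worth doing; and 2.e says the study's purpose is explained to patients. The design also makes a null result harder to read. Rescue morphine is offered to patients in either arm without adequate relief within 15 minutes, and 2.j keeps their data, so the arms may be drawn together at 30 and 60 minutes. Two sentences would cost nothing.

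Part of this stands. The verb in 2.d is stronger than G1 warrants, and the arithmetic is correct. The rest does not require a change. A broad motivating question and a pilot as the first step towards it can coexist, and ordinary research prose often puts the question that way. The harm depends on a future author overlooking G1; no stated rule leads there. A commitment to a confidence interval and a limit on reporting would belong in the analysis section or the protocol. Neither can be seen in full here, so their absence from 2.d shows no fault. The rescue point concerns how later pain scores are interpreted and applies whatever 2.d says.

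**Conclusion.** The mismatch is real but editorial, and no change to the plan follows. Under G1 as written, the trial supports a pilot-level estimate of the difference with a 95% CI of about ±0.64 SD, and the powered comparison is left to a later study. It could not establish comparable efficacy unless a margin near 0.9 SD were acceptable, and G1 does not claim that it could.

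The SD-unit figures rest on 20 complete patients per arm, a common SD and the conventional error rates named above; the millimetre figures also rest on an assumed scale and SD. The conclusion does not depend on any of these. It rests on the absence, in the text available, of any test, margin or decision rule that 2.d would distort. It would need another look if the protocol, or the part of section G not available here, planned to read a non-significant difference as equality.

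### VAS at 30 and 60 minutes can follow morphine rescue, and 2.j does not separate these scores from rescue-free ones; the rescue dose as printed also contradicts the study morphine dose

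*SAP*

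**What the plan says.** **Rescue.** Under Rescue Medication in E1: "Subjects that do not obtain adequate pain relief within 15 minutes of study drug administration will be offered rescue medication". The rule is not limited to one arm. The drug is "intravenous morphine sulphate at the same weight-based dose (0.01mg/kg; maximum 10 mg").

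**Study morphine dose.** E1 says patients are "randomized to either morphine (0.1mg/kg maximum dose of 10 mg) or ketamine (0.4 mg/kg, maximum dose of 40 mg"). Section 2.f says: "Participants in the opioid arm will receive 0.1 mg/kg of morphine up to 10 mg". Section 2.k says: "Participants in the opioid arm will receive 0.1 mg/kg IV of morphine (10 mg maximum").

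**Pain scores.** E1 and F2 place the follow-up VAS at 15, 30 and 60 minutes after study drug. F6 names change in VAS as an outcome and singles out no time point.

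**Rescued participants.** Section 2.j: "Participants who have inadequate pain relief and require rescue medication, or who have adverse events that require other treatment will have their data included", and this applies "even if study personnel are unable to complete the follow-up VAS scores at 15, 30, or 60 minutes".

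**What is compared.** Section 2.l: "The study is designed to compare a one-time dose only".

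**The concern.** Rescue becomes available at about 15 minutes, so two of the three follow-up scores can be taken after a participant has had extra morphine. In the ketamine arm this adds the comparator drug to the test drug; in the morphine arm it adds more of the same drug. Section 2.j brings these participants in without saying whether a score after rescue counts in the same way as one before it. It also does not distinguish a VAS missing because of rescue from one missing because of an adverse event.

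The order of events at 15 minutes is not fixed either. Nothing visible says that the 15-minute VAS comes before rescue, so even that score is not guaranteed to be free of rescue.

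G1 calls this a pilot looking for trends, with a full power analysis to follow if results are promising. What is at stake is a misread trend carried into the next study, not a failed formal test.

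The rescue-dose wording is a separate problem. It contradicts the stated study dose, and it bears on how far rescue could move the later scores.

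**Working it through.** **1. Nothing to reproduce.** The 20 per arm in 2.f comes from available funding (G1). The visible text states no SD, effect size, alpha, power, rescue rate or rescue effect. The figures below are illustrations on assumed values.

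**2. Formula.** Let d be the true single-dose difference in pain reduction (morphine minus ketamine), pK and pM the proportions below the rescue threshold in each arm, RK and RM the mean extra relief from rescue, and u the share of those offered rescue who accept it. Then

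observed difference = d − u × (pK × RK − pM × RM).

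The distortion is zero only when the two products are equal.

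**3. Assumptions.** SD of change 20 mm; mean reduction 30 mm on morphine and 15 mm on ketamine (d = 15 mm, the same at all times); rescue offered if the 15-minute reduction is under 13 mm; normal distribution; rescue fully effective by the later VAS.

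- pM = Φ((13 − 30)/20) = Φ(−0.85) = 0.198, about 4.0 of 20
- pK = Φ((13 − 15)/20) = Φ(−0.10) = 0.460, about 9.2 of 20
- pK − pM = 0.2625

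**4. Equal rescue effect in both arms (RK = RM = R).**

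| R (mm) | u = 1 | u = 0.5 |
|---|---|---|
| 2 | 15 − 0.53 = 14.5 | 15 − 0.26 = 14.7 |
| 15 | 15 − 3.94 = 11.1 | 15 − 1.97 = 13.0 |
| 30 | 15 − 7.88 = 7.1 | 15 − 3.94 = 11.1 |

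Over d of 10, 15 and 20 mm and thresholds of 10, 13 and 20 mm, with full uptake, the shrinkage is 3.0 to 3.9% for R = 2 mm and 22 to 58% for R = 15 to 30 mm.

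**5. Unequal rescue effect (same case, full uptake).**

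- RK = 5, RM = 25: 15 − (0.460 × 5 − 0.198 × 25) = 15 − (2.30 − 4.94) = 17.6 mm, so the difference widens.
- RK = 25, RM = 5: 15 − (11.50 − 0.99) = 4.5 mm.
- Break-even: RK/RM = pM/pK = 0.43. Below this ratio the difference widens.

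**6. No true difference.** With both means at 30 mm, 0.198 are rescued in each arm. Relief of 10 mm in one arm and 25 mm in the other gives a spurious 0.198 × 15 = 3.0 mm.

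**7. Scale.** With SD 20 mm and 20 per arm, the standard error of a difference is 20 × √(2/20) = 6.3 mm.

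**8. Dose wording.** Rescue Medication prints 0.01 mg/kg and calls it the same weight-based dose. E1, 2.f and 2.k give study morphine as 0.1 mg/kg. The ratio is 0.1/0.01 = 10. The cap is 10 mg in both places. The two statements cannot both stand.

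**The case against.** **The text is cut off, and 2.j is a retention rule.** The document stops mid-sentence in G2 and no analysis section is visible; a later rule for scores after rescue may exist. A reader might infer that the plan has no such rule, or that 2.j orders the scores to be used as observed. The text supports neither, so the point is conditional on use as observed.

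**Keeping rescued participants is good practice.** This stands in full. It avoids selective exclusion, and study drug plus rescue as needed is a legitimate comparison. It would be wrong to read this point as a call to drop those participants.

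**2.l describes the regimen.** A reader might infer that rescue breaks the one-dose statement, because a rescued morphine-arm participant gets morphine twice. It does not: 2.l goes on to say that study medication is given once, and rescue is a separate medication. What remains is narrower. The opening sentence of 2.l says what the study is designed to compare, and scores after rescue no longer reflect that single dose alone.

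**The size is assumed.** This stands. Rescue is offered, not imposed, so full uptake is an upper case, and half uptake halves the distortion. With small rescue relief the effect is negligible. The spurious 3.0 mm is under half a standard error (3.0/6.3 = 0.47). A reader might infer that the bias always runs towards no difference; the unequal-effect case shows otherwise.

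**Leading with 15 minutes would be a preference.** This stands too. F6 ranks no time point, and giving one priority is a trade-off that this point does not require.

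**Conclusion.** The point holds in conditional form. In the visible text, scores before and after rescue are not separated, so 30- and 60-minute VAS used as observed answers a different question from the single-dose comparison named in 2.l. Size and direction are not fixed by the documents. Under the assumptions shown, the effect runs from negligible (3 to 4% at about 2 mm of relief) to a true 15 mm appearing as 7.1 mm (30 mm of relief, full uptake), and it can also run the other way. In a pilot this is a matter of correct labelling and recording rather than a fatal flaw, but rescue times that are not recorded may not be recoverable later.

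The dose contradiction is firm and rests on no assumption: the rescue text differs tenfold from the study dose that it claims to match. The documents do not show which figure is intended.

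**What to change.** 1. Reconcile the rescue-dose wording under Rescue Medication with the study morphine dose in E1, 2.f and 2.k.
2. State that the 15-minute VAS is recorded before any rescue is given, leaving the rescue rule unchanged, and flag any case where rescue came first. Use this score as the rescue-free comparison of the single doses; it need not be ranked above the other time points.
3. Record rescue use and time, and report the proportion rescued by arm. Page 4 of the data form is not described, so the recording may already be in place; check this.
4. In 2.j, label the as-observed 30- and 60-minute comparisons as study drug plus rescue. Report VAS missing because of rescue separately from VAS missing because of adverse events.

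Cost: a few sentences in the SAP, slightly more recording, and one extra table. No added participants.
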